3.2.1	Enrolled Population	11
3.2.2	Safety Population	11
3.3	Patient Data and Study Conduct	11
3.3.1	Patient Disposition	11
3.3.2	Protocol Deviations	11
3.3.3	Demographic and Baseline Characteristics	11
3.3.4	Medical History	11
3.3.5	Prior and Concomitant Medications	12

3.3.6	Study Drug Exposure and Compliance.....	12
3.4	Efficacy Analyses.....	12
3.4.1	Primary Efficacy Endpoint	12
3.4.2	Secondary Efficacy Endpoints	13
3.4.3	Exploratory Efficacy Endpoints	13
3.5	Safety Analyses.....	13
3.5.1	Adverse Events (AEs)	14
3.5.2	AEs of Special Interest.....	14
3.5.3	Clinical Laboratory Tests.....	15
3.5.4	Vital Signs	15
3.5.5	Electrocardiograms.....	15
3.5.6	Physical Examinations	15
3.6	Data Safety Monitoring Board.....	15

LIST OF ABBREVIATIONS

Abbreviation	Definition
AdV	Adenovirus
AE	Adverse Event
ALT	Alanine Aminotransferase
AST	Aspartate Aminotransferase
ATC	Anatomical Therapeutic Chemical
AUC	Area under the Curve
BKV	BK Virus
CBC	Complete Blood Count
CMV	Cytomegalovirus
CRF	Case Report Form
CRS	Cytokine Release Syndrome
CSR	Clinical Study Report
CTCAE	Common Terminology Criteria for Adverse Events
DSMB	Data Safety Monitoring Board
EBV	Epstein-Barr Virus
ECG	Electrocardiogram
ET	Early Termination Visit
GVHD	Graft Versus Host Disease
GGT	Gamma-glutamyl Transferase
HBV	Hepatitis B virus
HCV	Hepatitis C virus
HCT	Hematopoietic Cell Transplant
HHV-6	Human Herpesvirus 6
HLA	Human Leukocyte Antigen
ICF	Informed Consent Form
JCV	JC Virus
LFT	Liver Function Test
MedDRA	Medical Dictionary for Regulatory Activities
NCI	National Cancer Institute
OL	Open Label
PBMC	Peripheral Blood Mononuclear Cell
PT	Preferred Term
Q	Every
QoL	Quality of Life
SAE	Serious Adverse Event
SAP	Statistical Analysis Plan
SAS	Statistical Analysis System
SoA	Schedule of Activities
SOC	System Organ Class
TEAE	Treatment-Emergent Adverse Event
TESAE	Treatment-Emergent Serious Adverse Event
WHO	World Health Organization

1 INTRODUCTION

The purpose of this Statistical Analysis Plan (SAP) is to provide a description of the statistical methods to be implemented for the analysis of data from the Phase 2 open label (OL) cohort of Protocol P-105-202. All the patients in the Phase 2 OL were enrolled, treated, and followed under Protocol Amendment 2 dated 7 April 2021. Data were collected under Protocol Amendment 2 Schedule of Activities ([Appendix 2](#)). The analysis will be based on Protocol Amendment 4 dated 19 October 2021. In addition, the clinically significant infections or episodes of end-organ disease were determined by the clinical investigators in Phase 2. [REDACTED]

The SAP will be finalized prior to Phase 2 database lock. Any deviations from the SAP after database lock will be documented in the final Clinical Study Report (CSR) for the Phase 2 OL cohort. [REDACTED].

2 STUDY OVERVIEW

2.1 Study Objectives

2.1.1 Primary Objective

The primary objective is to assess the efficacy of ALVR105 by the number of clinically significant infections or episodes of end-organ disease per patient due to AdV, BKV, CMV, EBV, HHV-6, or JCV through Week 14 as determined by the clinical investigators.

2.1.2 Secondary Objectives

The key secondary objective is to assess the efficacy of ALVR105 by the number of clinically significant infections or episodes of end-organ disease per patient due to AdV, BKV, CMV, EBV, HHV-6, or JCV through Week 26 as determined by the clinical investigators.

Other secondary objectives are as below:

- To assess the efficacy of ALVR105 by the number of clinically significant infections or episodes of end-organ disease per patient due to AdV, BKV, CMV, EBV, or HHV-6 due to each individual virus as determined by the clinical investigators through Week 14 and Week 26
- To assess the efficacy of ALVR105 in mean area under the curve (AUC) viral load for AdV, BKV, CMV, EBV, HHV-6, and JCV for each virus through Week 14 and Week 26

2.1.3 Exploratory Objectives

Exploratory objectives are as below:

- To determine the incidence and number of re-hospitalizations (following hospital discharge after HCT occurring after randomization) for AdV, BKV, CMV, EBV, HHV-6, or JCV infection or disease through Week 26
- To assess patient-reported quality of life (QoL) through Week 26

- To assess the efficacy of ALVR105 in the proportion of patients with undetectable AdV, BKV, CMV, EBV, HHV-6, or JCV viremia (defined as below the lower limit of quantification [LLOQ]) at Week 14
- To determine hospital length of stay (following initial hospital discharge) for AdV, BKV, CMV, EBV, HHV-6, or JCV infection or disease through Week 26
- To characterize virus specific T cells (VSTs) in patients who were administered ALVR105

2.1.4 Safety Objectives

The safety objectives are to characterize the safety and tolerability of ALVR105 when administered to patients at high-risk for AdV, BKV, CMV, EBV, HHV-6, or JCV following allogeneic HCT.

2.2 Study Design

2.2.1 Overview

This is a Phase 2/3, multicenter, randomized, double-blind, placebo-controlled trial to investigate the efficacy and safety of ALVR105 administered intravenously for the prevention of infection or disease due to AdV, BKV, CMV, EBV, HHV-6, or JCV in high-risk adult and pediatric patients after allogeneic HCT.

There are 2 parts to the study, a Phase 2 OL cohort [REDACTED]

[REDACTED] The first 25 to 35 patients (Phase 2 OL cohort) will receive ALVR105 for 14 weeks of OL dosing and will be followed for an additional 12 weeks. An assessment and optimization of study processes will be performed during the OL portion.

A review by the Data Safety Monitoring Board (DSMB) will be done when approximately 25 to 35 patients in the OL cohort have completed 30 days of treatment. At this time, an assessment of benefit, risk, and endorsement to proceed to Phase 3 will be undertaken. [REDACTED]

[REDACTED] Phase 2 OL patients already enrolled will continue in the open label cohort.

Once patients are assigned to ALVR105 in Phase 2, administration can begin as early as 15 days post-HCT as long as, in the Investigator's judgment, the patient has met the clinical engraftment criteria, and no later than 42 (+7) days post-HCT. AdV, BKV, CMV, EBV, HHV-6, and JCV viremia will be monitored as detailed in the Schedule of Activities (SoA) in the protocol.

Patients may receive all standard of care antiviral prophylaxis at their treating institutions including letermovir.

A summary of the Phase 2 OL cohort study design is shown in [Figure 1](#).

[figure not shown]
2.2.2 Study Drug

ALVR105 is a third-party, allogeneic, “off-the-shelf,” VST product with specificity for BKV, AdV, CMV, EBV, and HHV-6 (with additional cross-reactive specificity for JCV) that is cryopreserved and ready for immediate use.

2.2.3 Sample Size Determination

The first 25 to 35 patients (Phase 2 OL cohort) will receive ALVR105 for 14 weeks of OL dosing, after which they will be followed for an additional 12 weeks. A review by the DSMB will be done when approximately 25 to 35 patients in the OL cohort have completed 30 days of treatment. At this time, an assessment of benefit, risk, and endorsement to proceed to Phase 3 will be undertaken.

Figure 1. Study Flow Chart for Phase 2 OL Cohort

High-risk allo-HCT defined as: umbilical cord donor, haploidentical donor, MMRD, MUD, MMUD, recipient of T-cell depletion (ex vivo, alemtuzumab, ATG), persistent lymphopenia <180/mm³.

2.3 Study Endpoints

2.3.1 Primary Efficacy Endpoint

The primary endpoint is the number of clinically significant infections or episodes of end-organ disease per patient due to AdV, BKV, CMV, EBV, HHV-6, or JCV through Week 14.

2.3.2 Secondary Efficacy Endpoints

The key secondary endpoint is the number of clinically significant infections or episodes of end-organ disease per patient due to AdV, BKV, CMV, EBV, HHV-6, or JCV through Week 26.

The other secondary endpoints include:

- Clinically significant infections or episodes of end-organ disease per patient due to AdV, BKV, CMV, EBV, HHV-6, or JCV from each individual virus through Week 14 and Week 26 (6 endpoints each at Week 14 and Week 26)
- Mean viral load for AdV, BKV, CMV, EBV, HHV-6, and JCV for each individual virus through Week 14 and Week 26, obtained as AUC/number of days (6 endpoints each at Week 14 and Week 26)

2.3.3 Exploratory Efficacy Endpoints

The exploratory efficacy endpoints are:

- Proportion of patients with re-hospitalizations (defined as any hospitalization following hospital discharge from HCT or from any subsequent hospitalization before randomization) for AdV, BKV, CMV, EBV, HHV-6, or JCV infection or disease through Week 26
- For patients with re-hospitalizations, number of re-hospitalizations (defined as any hospitalization following hospital discharge from HCT or from any subsequent hospitalization before randomization) for AdV, BKV, CMV, EBV, HHV-6, or JCV infection or disease through Week 26
- Change in QoL, EQ-5D-5L, EQ-5D-Y, and EQ-5D-Y Proxy Version 1, through Week 26
- Undetectable AdV, BKV, CMV, EBV, HHV-6, or JCV viremia (defined as below the LLOQ for each virus) at Week 14
- Number of hospital days related to clinically significant AdV, BKV, CMV, EBV, HHV-6, or JCV infection or disease through Week 26
- Monitoring of anti-AdV, BKV, CMV, EBV, HHV-6, or JCV-specific T cell populations

Since the hospitalization and re-hospitalization data are not collected in the Phase 2 cohort, these endpoints will not be analyzed in this SAP. The anti-viral specific T cell data will not be analyzed in this SAP but reported separately.

2.3.4 Safety Endpoints

The safety endpoints include:

- Severity and incidence of acute graft versus host disease (aGVHD)
- Severity and incidence of chronic GVHD
- Severity and incidence of cytokine release syndrome
- Severity and incidence of graft failure
- Severity and incidence of clinically significant cytopenias
- Severity and incidence of renal dysfunction
- Effect on measures of engraftment
- Overall and non-relapse-related mortality

Data for effect on measures of engraftment were not collected in Phase 2 and will not be analyzed in this SAP. Safety assessments also include adverse events (AEs), vital signs, 12-lead electrocardiograms (ECGs), physical examination findings, and clinical laboratory evaluations (hematology, chemistry, and urinalysis).

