4. STUDY DESIGN

4.1. Overall Design

This is a Phase 2, multi-center, randomized, double-blind, placebo-controlled, multiple dosing, trial to investigate ALVR105 administered intravenously, with the first dose between 15 and 42 (+7) days after allogeneic HCT, followed by every 2-week infusions until Week 14, in comparison to matching placebo for the prevention of active replication and clearance of active viremia of AdV, BKV, CMV, EBV, HHV-6, and/or JCV in high-risk patients.

This study is comprised of an optional pre-screening period, a screening period, a treatment period, and a follow-up period. The optional pre-screening period is included to allow for the assessment of viral loads for patients who may potentially be eligible for participation in the study prior to actual screening. The screening period may begin at the time of HCT and may vary in length of up to 6 weeks. The treatment period is 14 weeks, and the follow-up period is approximately 12 weeks. Overall, the total duration patient participation in the study is approximately 28 to 32 weeks (up to 6 weeks for screening, 14 weeks of treatment, and 12 weeks of follow-up). The overall enrollment period is anticipated to be approximately 12 months.

Patients will also receive a telephone call follow-up approximately 52 weeks after their last study visit to assess mortality.

There are 3 cohorts (Cohort Open Label [OL],

The first 25 to 35 patients (Cohort OL) will receive ALVR105 for 30 days of open-label dosing to assess and optimize processes. A review by the Data Safety Monitoring Board (DSMB) will be done when approximately 30 patients have completed 30 days of treatment. At this time an assessment of benefit, risk, and process will be done, and study optimization will be considered.

Open label patients will continue in the open label arm.

Patients will be tested at the first assessment during Screening by the central laboratory for AdV, BKV, CMV, EBV, HHV-6, and JCV viremia using polymerase chain reaction (PCR) assays for each virus. Patients will then be tested weekly during Screening until treatment assignment. In **Cohort OL**, patients may test positive or negative for AdV, BKV, CMV, EBV, HHV-6, and/or JCV viremia.

ohort OL will also include a 50% cap for letermovir prophylaxis; Sponsor can revisit this limit based on on-going assessment of feasibility. With respect to other

prophylaxis treatments see the inclusion criteria ([Section 5.1](#)).

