8.1.4. Follow-up period

The follow-up period is for 12 weeks with monthly visits. A telephone follow-up call will occur approximately 12 months (~52 weeks) after Week 26.

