3.3 Patient Data and Study Conduct

3.3.1 *Patient Disposition*

Patient disposition information will be summarized using the Enrolled Population. The numbers and percentages of patients who were screened, screen failure along with the reasons of screen failure, not dosed, dosed, completed study drug, discontinued study drug early along with the reasons for early discontinuation of study drug, completed the study, and discontinued the study early along with the reasons for early discontinuation of study, received a Week 52 follow-up call will be summarized.

The numbers and percentages of patients in Safety Population with reason for exclusion will also be summarized.

By-patient listings will also be provided for patient disposition, screen failures, patients who were enrolled but not dosed, and reason for exclusion from analysis population.

3.3.2 *Protocol Deviations*

The numbers and percentages of patients with protocol deviations by deviation category will be summarized on Safety Population. All protocol deviations will be determined prior to database lock and listed by patient.

3.3.3 *Demographic and Baseline Characteristics*

Demographic (age, sex, race, and ethnicity) and baseline characteristics (height, weight, BMI, and childbearing potential at baseline) will be summarized with descriptive statistics or counts and percentages of patients as appropriate for safety population.

The following disease characteristics will also be summarized using frequencies and percentages: diagnosis, donor type, HLA alleles from the study patient, the allogeneic HCT donor(s), and the VST donor(s) as well as the number of shared alleles among these individuals, pre-conditioning therapy received, CMV serostatus at baseline of donor and recipient, letermovir use at Baseline, presence of Baseline viremia (based on central lab) and level of conditioning (myeloablative, reduced intensity, and non-myeloablative). A by-patient listing will be provided.

3.3.4 *Medical History*

Medical history will be coded to system organ class and preferred term using the Medical Dictionary for Regulatory Activities (MedDRA). The numbers and percentages of patients with

medical history by system organ class and preferred term will be summarized for safety population.

A by-patient listing of medical history will be provided.

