3.5 Safety Analyses

Safety data will be summarized based on the Safety Population. Categorical endpoints will be summarized using the number and percentage of patients within each category. Continuous endpoints will be summarized descriptively with summary statistics (number of non-missing observations, arithmetic mean, standard deviation, median, minimum, and maximum).

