3.5.1 Adverse Events (AEs)

All AEs will be coded to system organ class and preferred term using MedDRA. Treatment emergent adverse events (TEAEs) are defined as an AE with onset or worsening on or after the first dose of study treatment through the end of study (i.e., Week 26).

An overall summary of AEs will be provided with the number and percentage of patients who experienced at least 1 AE or TEAE in the following categories:

- Any TEAEs
- Any TEAEs by severity
- Any treatment-related TEAEs
- Any AEs of special interest (AESIs)
- Any treatment-emergent AESI (TEAESIs)
- Any treatment-related TEEAESIs
- Any serious AEs (SAEs)
- Any treatment-emergent serious AEs (TESAEs)
- Any treatment-related TESAEs
- Any TEAEs leading to discontinuation of study treatment
- Any TEAEs leading to discontinuation of study
- Any AEs leading to death

The numbers and percentages of patients will also be presented by system organ class (SOC) and preferred term (PT) for each of the TEAE categories in the summary. Patients with multiple AEs will be counted only once per SOC and PT. The number and percentage of patients with TEAEs will be tabulated by PT and by the highest CTCAE Grade.

Listings will be presented specifically for any AEs, deaths, SAEs, and TEAEs leading to discontinuation of study treatment and study.

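### The SAP lists overall and non-relapse mortality as safety endpoints but plans no survival estimate, uses the mortality call only as a disposition count, and labels that call Week 52 although it falls at about Week 78 for completers

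*SAP*

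**What the plan says.** SAP 2.3.4 includes "Overall and non-relapse-related mortality" in its list of safety endpoints. It gives no time horizon and no rule for classing a death as non-relapse. The same section drops one endpoint for lack of data: "Data for effect on measures of engraftment were not collected in Phase 2 and will not be analyzed in this SAP". Mortality is not dropped, so it is meant to be analysed.

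SAP 3.5.2 names outputs for acute and chronic GVHD, CRS, infusion-related events and graft failure. No section does this for mortality. Three provisions remain:

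- the general rule in SAP 3.5: "Categorical endpoints will be summarized using the number and percentage of patients within each category";
- a row in the adverse event overview in SAP 3.5.1: "Any AEs leading to death";
- listings, also in SAP 3.5.1: "Listings will be presented specifically for any AEs, deaths, SAEs, and TEAEs leading to discontinuation of study treatment and study".

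On the telephone call, Protocol 4.1 states: "Patients will also receive a telephone call follow-up approximately 52 weeks after their last study visit to assess mortality". Protocol 8.1.4 gives the timing as: "A telephone follow-up call will occur approximately 12 months (~52 weeks) after Week 26". The SAP mentions the call once, in the disposition summary of section 3.3.1, where the number of patients who "received a Week 52 follow-up call will be summarized".

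**The concern.** After allogeneic transplant, death is the least ambiguous outcome and relapse is a major reason for it, so how mortality is estimated matters. Three things look wrong.

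1. The only estimate on offer is deaths divided by patients treated. A patient who leaves at Week 6 and is not known to have died stays in the denominator as a survivor for the whole period.
2. The protocol asks for a further contact whose stated purpose is to assess mortality, and the SAP plans no estimate from it.
3. The SAP's week label for that contact does not agree with the protocol's timing.

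At stake is the quality of a safety estimate in the open-label cohort, including whether two programmers would produce the same non-relapse figure. No hypothesis test is involved.

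**Working it through.** **Timing of the call.** The SAP's own figure is Week 52. SAP 3.1.1 counts study days from first dose as Day 1, and SAP Appendix 1 puts Week 26 at Day 183. The call's study week is the anchor week + 52:

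| Anchor | Study week of call |
|---|---|
| First dose (Day 1) | 0 + 52 = 52 |
| Week 14, last visit of a patient who leaves then | 14 + 52 = 66 |
| Week 20, last visit of a patient who leaves then | 20 + 52 = 72 |
| Week 26 visit | 26 + 52 = 78 |

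Week 52 is reproduced only by counting from first dose, and the protocol does not anchor the call there. On its anchor a completer is called at about Day 183 + 364 = Day 547, which is Week 78. The label is out by 78 − 52 = 26 weeks for completers and by less for early leavers.

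**Size of the bias in a crude percentage.** The documents give no mortality or withdrawal rates, so these inputs are assumptions: true mortality by Week 26 of m = 15%; withdrawal from the study by Week 26 of d = 10%, 20% or 30%; withdrawal independent of death; deaths after withdrawal not captured.

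With constant hazards, a = −ln(1 − m) and b = −ln(1 − d), and the expected crude proportion is a/(a + b) × [1 − (1 − m)(1 − d)]. Here a = 0.1625.

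| d | b | Crude proportion | Understatement (points) | Patients in 30 |
|---|---|---|---|---|
| 10% | 0.1054 | 0.1625/0.2679 × 0.235 = 14.3% | 0.7 | 0.2 |
| 20% | 0.2231 | 0.1625/0.3857 × 0.320 = 13.5% | 1.5 | 0.5 |
| 30% | 0.3567 | 0.1625/0.5192 × 0.405 = 12.7% | 2.3 | 0.7 |

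As a check, uniform event and withdrawal times give an understatement of m × d/2, that is 0.75, 1.50 and 2.25 points. Over a wider range with constant hazards (m and d each 10% to 30%) it runs from 0.5 to 4.5 points.

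**Precision.** For comparison, 3 deaths in 30 patients is 10%, with exact 95% confidence interval 2.1% to 26.5%. Six in 30 is 20%, with interval 7.7% to 38.6%. The SAP plans no interval for mortality.

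**What the call could add.** It comes 52 weeks after the last visit, so for anyone reached it falls later than Week 26. It can therefore supply Week 26 survival status for early leavers as well as later follow-up for completers.

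**The case against.** The strongest reply is that crude proportions follow the protocol. It words its mortality endpoints as a proportion and an incidence, sets the objective on non-relapse mortality at Week 26, and reserves Kaplan-Meier for time-to-event endpoints (Protocol 9.4.1). No endpoint in either document is mortality at the call. Patients who only stop treatment stay in follow-up (Protocol 7.1 and 7.3), and the bias is under one patient in 30 in the 15% example. This stands as a limit on importance. It does not supply a horizon, a non-relapse rule or an interval, and it leaves survival data collected at the call without an estimate.

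A reader might infer four stronger things that the documents do not support:

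- **That the crude count mishandles competing risks.** It does not. Patients who die of relapse stay in the denominator, and with complete follow-up the crude proportion equals the Aalen-Johansen estimate. The bias comes only from incomplete follow-up.
- **That deaths after Week 26 will never be reported.** The Week 26 limit belongs to treatment-emergent events (SAP 3.5.1). The death row is not restricted to those and the listing has no stated cut-off, so late deaths could appear there.
- **That the label misplaces survival status by 26 weeks.** The label heads a disposition count, and no survival time is computed from it. It may be shorthand for 52 weeks after the last visit.
- **That adverse event pages must miss deaths.** Protocol 10.3.1 excludes expected progression of the disease being studied. In a trial of viral prevention this does not plainly exclude relapse deaths. Using several sources is prudent, but a gap is not shown.

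There is also a question of version. The SAP says patients were followed under Amendment 2 and analysed under Amendment 4, and the protocol text supplied does not show its amendment number. A later change to the call cannot be ruled out.

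**Conclusion.** The point holds as a gap in the analysis plan, of modest size. A listed endpoint that was not dropped has only a generic crude percentage, an adverse event row and a listing. The call made to assess mortality yields a count of calls and no survival estimate. Its label is 26 weeks early for completers on the SAP's own day scale.

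The understatement of about 0.7 to 2.3 points rests on assumed mortality of 15%, assumed withdrawal of 10% to 30%, and withdrawal unrelated to prognosis. If sicker patients withdraw more, the understatement is larger and Kaplan-Meier does not fully remove it, which is a further reason to use the call data. Sampling error at 25 to 35 patients far exceeds this bias, so the change improves the estimate without altering what the cohort can show.

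**What to change.** In SAP 3.5, add a mortality section that does the following:

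- takes deaths from adverse event, disposition and call records together;
- states when a death counts as non-relapse;
- estimates overall mortality by Kaplan-Meier from first dose, censoring at the date last known alive, with 95% confidence intervals at Week 26 and through the call;
- reports non-relapse mortality to Week 26 as cumulative incidence (Aalen-Johansen) with relapse-related death as the competing event, also with 95% confidence intervals, and extends it through the call only if cause of death or relapse status is recorded there. The protocol describes the call only as a mortality contact, so this needs confirming first.

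In SAP 3.3.1, relabel the call as 52 weeks after the last study visit (about Week 78 for completers), after checking the timing against the governing amendment.

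The cost is SAP wording, one table and one figure. No new visit is needed. The intervals will be wide at 25 to 35 patients and should be shown as such.
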